Inclusion Criteria	Exclusion Criteria
Caregivers of a child between ages 9-18 who has either not received any HPV vaccine doses or has received only initial HPV dose	Caregivers whose child has completed additional HPV vaccine doses
Receives care at Adelante Healthcare Mesa	
Fluent in English and/or Spanish	
Willing to provide informed consent	

BIOSCIENCE INSTRUCTIONS AND TEMPLATE

NUMBER	DATE	PAGE
HRP-503b	3/31/2020	2 of 4

5 Number of Participants

90 participants will be enrolled in the study; 45 in the control group / 45 in the intervention group

6 Recruitment Methods

The study research assistants (RA) will work directly with the clinic during the study enrollment period to generate a list of all patients (and their caregivers) who may be eligible to participate in the study. Adelante office staff will search patients' online medical files to determine which individuals are age-eligible for the vaccine who have either 1) not initiated the vaccine series and/or 2) have only completed one of the HPV vaccine doses. They will generate a list of eligible patients with caregiver contact information to the RA.

The RA will use a vacant office space for all recruitment and enrollment activities. To initiate contact with potential participants, she will send a letter to caregivers of children eligible for HPV vaccine, inviting them to take part in a study about HPV vaccine intentions. The letter will contain study-specific phone number that will reach RA's office directly. RA will screen caregivers for eligibility and notify clinic staff of all patients/caregivers eligible for study. Caregivers will work with clinic staff to schedule an office visit. When the clinic staff schedules the patient's visit, they will ask caregivers to stay an addition 15-20 minutes after their scheduled appointment to complete the study informed consent and baseline surveys.

7 Study Timelines

We anticipate participants being a part of the study for up to 8 months. We expect that individuals will spend up to 2 hours (1 hour on 2 days) on completing study surveys, one on the first day of the study and another after six months. They will also spend time taking their child to receive the additional HPV vaccine doses.

8 Procedures Involved

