The project utilizes a software (REDCap) which randomizes individuals into intervention and control groups, using permuted block randomization. As participants enroll in the study, they will be given a study identification number (e.g. 1,2,3). Both the intervention and control groups will complete baseline surveys.

Control group participants will receive standard care and will be expected to return to Adelante Healthcare Mesa to receive the additional HPV vaccine booster doses. Intervention group participants will be referred to receive the additional HPV vaccine doses at their community pharmacy. At post-intervention, intervention participants will be asked if their children completed the HPV vaccine series.

Primary behavioral outcome: At the end of the 16-month intervention, PI will ask clinic staff to report HPV vaccination dose completion (for vaccine doses 1,2,3) for all study participants.

Follow-up Survey Data Collection: RA will call all participants and administer follow-up survey to measure potential changes in DOI theoretical constructs (see baseline survey).

Qualitative telephone in-depth interviews: To qualitatively explore intervention feasibility and acceptability, PI will conduct telephone interviews with patients, patients' caregivers, clinic primary care providers, and clinic pharmacists.

- In-depth interview with Caregivers and/or Young Adult Patients: PI will conduct telephone interviews with caregivers from the control group (standard care) and from the intervention group (pharmacist-administered HPV vaccination) related to their experiences taking part in the study.
- In-Depth interviews with Providers and Pharmacists: Researchers will conduct telephone interviews with all the clinic's participating primary health care providers and office manager (n= 4) and local pharmacists who work at pharmacies where patients were referred to receive the HPV vaccine (n=4) to explore their acceptability and perceived feasibility of the intervention. They will be asked how the intervention impacted the quality of patient care, ways in which the intervention impacted patient flow within the clinic, how satisfied they were with the intervention, and perceived fit of the intervention within their workplace.

Participant Incentives: Research participants will receive e-gift card incentives (of their choosing from Tango Card, Inc) for completing study surveys (\$20 dollars per survey completed) and for participating in telephone interviews (\$30).

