9 Withdrawal of Participants

There are no anticipated circumstances under which participants will be withdrawn from the research study without their consent.

If participants choose to no longer take part in this study, they are asked to contact the PI ([name], [contact]) to notify her that they will no longer be involved in the study. The PI will remove and destroy all participant data from the study.

BIOSCIENCE INSTRUCTIONS AND TEMPLATE

NUMBER	DATE	PAGE
HRP-503b	3/31/2020	3 of 4

10 Risks to Participants

There are no foreseeable risks to research participants. Risks of the HPV vaccine (a non-virus vaccine –which utilizes a protein which looks similar to HPV) include a fever, pain at injection site, and a headache. A much less common side effect of the vaccine is fainting within 15 minutes of injection. For this reason /risk, patients are told to remain at the clinic/pharmacy for an additional 15 minutes after they receive the vaccine to ensure that they are safe to leave.

11 Potential Benefits to Participants

HPV vaccine age-eligible children will complete the HPV vaccine series, thus preventing the risk of HPV-related cancers. Also, intervention participants will learn more about the role of the community pharmacist in administering vaccines and vaccine booster doses. This may help aid in the completion of vaccine series without having to schedule and revisit primary care providers' offices.

12 Setting

This study will be conducted at Adelante Healthcare Mesa, a local federally qualified health center. Intervention participants will be referred to receive additional HPV vaccine booster shots with their community pharmacists. Pharmacists are currently licensed to administer the HPV vaccine.

13 Multi-Site Research

NA

14 Resources Available

This clinically based study will take place at Adelante Healthcare Mesa, a Federally Qualified Health Center (FQHC) which predominantly serves ethnic/racial minority, low-income populations.

15 Prior Approvals

We have received prior approval and secured an MOU with Adelante Healthcare Mesa to conduct this study.

16 Data Management and Confidentiality
Data Analysis:
Aim 1 Data Analysis: Assessing Preliminary Efficacy.

The specific aim of the proposed project is to investigate the effect of CPVAC on HPV vaccination completion rate compared with primary care provider (Aim 1).

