Patient-related outcomes: Two proportion Z tests will be used to examine the proportion differences in HPV vaccination completion between CPVAC and primary care provider (PCP) groups. We will also compare which medical professionals completed the vaccine doses. We will create codes for various health care professionals (e.g. nurse, nurse practitioner, physician, pharmacist, etc.) to differentiate who administered the vaccine. The HPV completion status will be classified as dichotomous variable (0 = no; 1 = yes). Independent variables will be classified as either categorical or continuous scale: age, gender, race; location, HPV vaccine dose (1, 2, 3, etc); provider types (PCP vs pharmacist); facility type/place of service (health clinic vs. pharmacy). Multiple logistic regression with stepwise selection procedures will be used to identify whether these independent variables are associated with HPV completion status.

Psychosocial Constructs Data Analysis: Baseline characteristics of the study participants will be summarized using descriptive statistics. Multiple logistic regression will be used to investigate whether psychosocial factors (e.g. intention, norms, efficacy) relate to HPV vaccine completion (yes/no). General linear models or Mann-Whitney U tests will be used to test mean or median differences for self-efficacy and response-efficacy to complete the vaccine series between CPVAC and PCP groups.

Missing Data: We will conduct sensitivity analyses including imputation methods and completer-only analyses. All statistical procedures and analyses will be performed in SPSS software.

BIOSCIENCE INSTRUCTIONS AND TEMPLATE

NUMBER	DATE	PAGE
HRP-503b	3/31/2020	4 of 4

Aim 2 Data Analysis: Qualitatively exploring feasibility and acceptability of CPVAC

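### The stepwise model for completion lists predictors that arise after randomisation (dose number, place of service and, on one reading, provider type) and does not explicitly name randomised arm

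*Combined protocol and SAP*

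**What the plan says.** Section 16 states Aim 1 as to "investigate the effect of CPVAC on HPV vaccination completion rate compared with primary care provider (Aim 1"). It plans two separate analyses of completion, which is coded yes/no.

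- **Comparison by group:** "Two proportion Z tests will be used to examine the proportion differences in HPV vaccination completion between CPVAC and primary care provider (PCP) groups".
- **Regression:** the independent variables are age, gender, race, location and then "HPV vaccine dose (1, 2, 3, etc); provider types (PCP vs pharmacist); facility type/place of service (health clinic vs. pharmacy"). The next sentence reads "Multiple logistic regression with stepwise selection procedures will be used to identify whether these independent variables are associated with HPV completion status".

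The same paragraph says of vaccinators: "We will create codes for various health care professionals (e.g. nurse, nurse practitioner, physician, pharmacist, etc.) to differentiate who administered the vaccine".

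Three other places bear on what these variables can mean. Section 4 admits caregivers of a child who "has either not received any HPV vaccine doses or has received only initial HPV dose". Section 8 says "Intervention group participants will be referred to receive the additional HPV vaccine doses at their community pharmacy", and has clinic staff "report HPV vaccination dose completion (for vaccine doses 1,2,3) for all study participants".

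The documents do not define the dose variable, the unit of analysis, the number of doses that makes a series complete, or the code for a child with no further dose.

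**The concern.** A regression meant to show what is associated with completion should use predictors fixed before the outcome begins to unfold. Dose number and place of service are not, and provider type may not be. Dose number appears to come from the same dose record that determines the outcome. Place of service, and provider type if it means the person who gave the vaccine, exist for the additional doses only in children who came back.

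Two things are at stake. First, the model may be degenerate: unstable odds ratios, and a selection step that says only that children with more doses completed. Second, if an analyst removes dose number to obtain a fit, the remaining receipt variables can make pharmacists look linked to completion when CPVAC did nothing. The randomised contrast, which is the subject of Aim 1, is not explicitly in the model to act as a check.

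**Working it through.** The plan gives no figure for this model, so there is none to reproduce. From the documents: 90 children, 45 per arm, 0 or 1 dose at entry. Everything else below is an assumption: a complete series is two or three doses, and completion, pharmacy use and dose mix are varied over ranges.

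**1. When each predictor is fixed.** Age, gender and race are known at entry. Dose values 2 and 3 cannot be entry status, because entry allows only 0 or 1. Place of service is known only when a dose is given. Provider type is also a receipt variable if it means the person who vaccinated. Intervention families are referred to a pharmacy, so assignment and receipt can differ.

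**2. Dose number as a count of doses received.** A child with 0 or 1 dose is a non-completer. A child with 3 is a completer. A child with 2 is either, depending on the series. So the score (dose − 2) is never positive for a non-completer with at most two doses and never negative for a completer. The likelihood keeps rising as the coefficient grows, which is separation.
- Simulation (12 scenarios, 500 trials each, every child starting with one dose, with and without an arm effect): the model with age, gender and dose count separated in 100% of trials in every scenario. Separation was complete when all children needed two doses, all needed three, or age decided. It was quasi-complete when the two series were mixed independently of the covariates.
- One mixed example (non-completers/completers): 1 dose 40/0, 2 doses 2/33, 3 doses 0/15. The dose coefficient was 8.8, 13.8, 18.8, 23.8 and 28.8 after 5, 10, 15, 20 and 25 iterations. Its standard error grew from about 2 to over 42,000.
- In a wider null simulation (102 scenarios, 4,000 trials each), dose had a larger likelihood ratio than provider type in every trial. Provider type, given dose, then passed p<0.05 in 0–9% of trials.

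**3. Dose number as an index in dose-level rows.**
- *Categorical index, child's completion as outcome:* the final-dose row exists only for completers. At least one level was all-completer in 99.5–100% of simulated trials, which is quasi-separation.
- *Continuous index, same outcome:* this separates only if no non-completer has a second dose. With completion c, share t needing three doses, and share q of incomplete three-dose children having two, the probability is about [1 − (1 − c)·t·q]^90. For t = 0.4 and q = 0.3:
  - c = 0.3: 0.916^90 = 0.0004
  - c = 0.5: 0.94^90 = 0.004
  - c = 0.7: 0.964^90 = 0.037
  
  It rises when second doses are rare among non-completers (q = 0.1, c = 0.5: 0.98^90 = 0.16). It is 1 if every child needs two doses (t = 0).
- *One row per scheduled additional dose, outcome that dose given or not:* the index separated in at most 0.1% of simulated trials.

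In all three, the index is post-randomisation and rows from one child are correlated.

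**4. Provider type with dose number dropped.** Assume no arm effect, c = 0.5, t = 0.4, q = 0.3, and pharmacy use among returning children of 50% (intervention) and 5% (control), average 27.5%.
- Completers: 90 × 0.5 = 45. Non-completers with a further dose: 45 × 0.4 × 0.3 = 5.4. No further dose: 90 − 50.4 = 39.6, all non-completers.
- Pharmacist: 45 × 0.275 = 12.4 completers of 50.4 × 0.275 = 13.9 children, or 89%.
- Never-returners coded non-pharmacist: (45 − 12.4)/(90 − 13.9) = 32.6/76.1 = 43%.

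That is 89% against 43% with no CPVAC effect. Provider type passed p<0.05 in 94% of simulated trials here, and in 9–100% over all assumed inputs.
- Never-returners set to missing: 50.4 children remain, with 45/50.4 = 89% completion for either provider type. The gap disappears, but the 39.6 excluded children are all non-completers and the comparison is no longer randomised.

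The Z test by arm rejected in 4–7% of trials throughout the null simulations.

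**5. After the change.** With completion on arm, age and gender, separation occurred in 0% of trials in all 12 scenarios of step 2.

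**The case against.** The strongest reply has four parts.

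- **The dose variable is undefined.** A reader might infer that the planned fit must separate. The documents do not support that: Section 16 allows either categorical or continuous variables and states no unit of analysis. Section 8's reporting by dose even fits a per-dose outcome. As step 3 shows, separation is then often absent. This stands, and limits the separation claim to a count, or to a categorical index with the child's completion as outcome.
- **The PCP-versus-pharmacist variable may be the arm.** Section 16 calls the control group the PCP group, and Section 8 describes the intervention as pharmacist-administered vaccination. The vaccinator codes have more levels, and a two-level variable has no place for a nurse. This also stands as a possible reading, so one cannot say flatly that arm is omitted, only that it is not explicitly named. Place of service remains a receipt variable either way.
- **The false pharmacist signal needs two analyst steps that the plan does not state:** dropping dose number, and coding never-returners as non-pharmacist. Correct. Its frequency depends wholly on assumed inputs, so it is a risk to close off and not a forecast for this trial.
- **The model is exploratory, in a pilot, and separation shows itself in the output.** This lowers the severity. It does not make a predictor that may encode the outcome useful, and bias from receipt variables does not show itself in the same way.

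**Conclusion.** The point holds in a limited form. On any reading, values 2 and 3 of dose number, and place of service for the additional doses, arise after randomisation; provider type does too if it means the vaccinator. Place and vaccinator have no natural value for children with no further dose, none of whom can be completers. If dose number counts doses received, the fit separates under every two- and three-dose mix tried. On the other readings separation is conditional, but timing and clustering remain problems.

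A reader might go further and infer that Aim 1 is left unanswered or its test is biased. The documents do not support that: the Z test compares the groups directly and does not use these variables. The harm is confined to a secondary model, and the defect is minor to moderate. The conclusion assumes that a complete series needs at least two doses. The simulated frequencies also rest on assumed completion, pharmacy use and dose mix.

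**What to change.** Change the wording of Section 16 as follows.

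- Keep the Z test as it is.
- Remove dose number received, provider type and place of service as predictors of completion, and location too if it means place of vaccination.
- Fit one participant-level logistic model, analysed as randomised, with randomised arm forced in and a few pre-specified baseline covariates: doses at entry (0 or 1), age, gender, race/ethnicity.
- If the PCP-versus-pharmacist variable meant assigned group, rename it randomised arm.
- Report who gave the doses and where, descriptively by arm, with no further dose as its own category. This extends the comparison of medical professionals already planned.

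The cost is an edit to one section, with no added participants or data. The downside is that the model no longer screens provider or place as predictors; the descriptive table covers that question.

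### The between-arm comparison of self-efficacy and response-efficacy does not specify time point, outcome form, baseline adjustment or choice of test; prespecifying ANCOVA would gain precision at no cost.

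*Combined protocol and SAP*

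**What the plan says.** Section 8 (Procedures Involved) sets up a two-wave survey. At entry, "Both the intervention and control groups will complete baseline surveys". Later, "RA will call all participants and administer follow-up survey to measure potential changes in DOI theoretical constructs", and that sentence refers the reader back to the baseline survey for the constructs. Section 7 (Study Timelines) times the surveys: "one on the first day of the study and another after six months".

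The between-arm analysis is a single sentence in Section 16, under the psychosocial constructs heading: "General linear models or Mann-Whitney U tests will be used to test mean or median differences for self-efficacy and response-efficacy", comparing the CPVAC and PCP groups. It names no time point, no outcome form, no covariate and no rule for choosing between the two methods. The only use of baseline data stated in that paragraph is descriptive: "Baseline characteristics of the study participants will be summarized using descriptive statistics".

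Section 5 gives the size: "90 participants will be enrolled in the study; 45 in the control group / 45 in the intervention group". Section 8 describes software "which randomizes individuals into intervention and control groups, using permuted block randomization". No stratification of the randomisation by psychosocial score is described.

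**The concern.** The survey is designed to measure change, yet no analysis sentence says how the baseline score enters the comparison between arms. Three things are at stake.

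- **Precision.** A baseline measurement of the same construct usually predicts the follow-up score. A comparison that ignores it is noisier than the data allow.
- **Chance imbalance.** With 45 per arm and no stratification on these scores, the arms can differ at baseline by chance. Part of that gap passes into an unadjusted follow-up difference.
- **Open choices.** Because the method, outcome form and adjustment are not fixed, they could be settled after the data are seen.

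**Working it through.** The documents give no power calculation, alpha, SD, effect size or baseline/follow-up correlation for these scores, so there is no figure of the plan's own to reproduce.

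**Inputs from the documents:** 45 per arm (Section 5); surveys on day one and after six months (Section 7).

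**Assumed for illustration:** two-sided alpha 0.05; true difference 0.5 SD; score SD of 1 at both surveys; complete follow-up; correlation r between baseline and follow-up of 0.3, 0.5 or 0.7.

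**Step 1: follow-up scores alone.** SE = sqrt(2/45) = 0.211 SD. The noncentrality is 0.5/0.211 = 2.37, and noncentral-t power is 65%. Mann-Whitney on normally distributed scores gave about 63% in a 20,000-replicate simulation.

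**Step 2: ANCOVA.** The residual variance is multiplied by (1 - r²), so SE = sqrt(1 - r²) × 0.211, and the 90 participants act like 90/(1 - r²) analysed without adjustment.

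| r | 1 - r² | SE (SD) | Power, noncentral t | Equivalent unadjusted N | Effect detectable with 80% power (normal approx.) |
|---|---|---|---|---|---|
| unadjusted | 1.00 | 0.211 | 65% | 90 | 0.59 SD |
| 0.3 | 0.91 | 0.201 | 69% | 90/0.91 = 99 | 0.56 SD |
| 0.5 | 0.75 | 0.183 | 77% | 90/0.75 = 120 | 0.51 SD |
| 0.7 | 0.51 | 0.151 | 91% | 90/0.51 = 176 | 0.42 SD |

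The normal approximation gives power of 66%, 70%, 78% and 91% for the same four rows.

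**Step 3: chance baseline gap.** The difference in baseline means also has SD 0.211. The probability of a gap above 0.3 SD in either direction is 2 × (1 - Φ(0.3/0.211)) = 0.155, about 15%. The expected shift in the unadjusted follow-up difference is r times the gap: 0.3 × 0.3 = 0.09, 0.5 × 0.3 = 0.15 and 0.7 × 0.3 = 0.21 SD. In simulation, among trials with a gap near 0.3 SD, the shifts were 0.09, 0.14 and 0.21 SD. The ANCOVA estimate shifted by less than 0.01 SD.

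**Step 4: validity.** With no true difference, the simulated rejection rates of the t test, Mann-Whitney and ANCOVA all lay between 4.8% and 5.2%.

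**Step 5: if change scores were meant.** Their variance is 2(1 - r) times the score variance: 1.4, 1.0 and 0.6 at the three r values, against 0.91, 0.75 and 0.51 for ANCOVA. The excess is 2(1 - r) - (1 - r²) = (1 - r)², which is never negative. Change scores are noisier than follow-up scores alone when r is below 0.5. They are never more precise than ANCOVA, apart from the one degree of freedom that ANCOVA spends on the slope.

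**The case against.** The strongest reply is that the plan is silent, not wrong. A reader might infer from Section 16 that follow-up scores will be compared with baseline deliberately left out. The text does not support that. It lists no covariates for this analysis at all, and general linear models include ANCOVA. Nothing says that baseline will be adjusted for, and nothing says that it will not. This part of the objection stands, and the point is therefore one of under-specification.

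Three further limits also stand.

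- Section 8 speaks of changes, so change scores may be intended. A reader might infer that Mann-Whitney cannot use baseline at all, but it can be run on change scores. What it cannot do is adjust for a covariate.
- A reader might infer that a chance baseline gap passes in full into the result, or that the test is invalid. Only r times the gap is carried over, and unconditional type I error holds.
- That self-efficacy and response-efficacy are measured at both surveys is an inference. The survey is not in the documents, and Section 8 refers only to DOI constructs.

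The objection does not remove the need for a change. A model class that could include the baseline score is not a statement that it will. The same paragraph of analysis plans lists its independent variables for the completion model but none here. ANCOVA is also the more precise choice whichever outcome form was meant.

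**Conclusion.** The point holds as a gap in specification with a better method ready to hand. If follow-up scores are compared unadjusted, power for a 0.5 SD difference is about 65%, against about 69%, 77% and 91% with ANCOVA at r = 0.3, 0.5 and 0.7. There is also about a 15% chance of a baseline gap above 0.3 SD that would go uncorrected. The size of the gain depends almost entirely on r, which the documents do not give; at r = 0.3 it is modest. The power figures further assume two-sided 5% alpha, no loss to follow-up and matching items in both surveys.

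Severity is low. This is a secondary psychosocial analysis in a pilot, and the primary outcome, completion of the vaccine series, is unaffected.

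**What to change.** Replace the sentence in Section 16 with a statement that:

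- each six-month construct score is analysed by a linear model with randomised arm and the same construct's baseline score as covariate;
- the result is reported as the adjusted mean difference with its 95% confidence interval;
- if scores are skewed, robust standard errors or a rank-based ANCOVA are used in place of an unadjusted Mann-Whitney test, with the rule for switching stated in advance.

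Confirm in the same place that the self-efficacy and response-efficacy items are in both surveys.

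The cost is one or two sentences of text. If the items are in both surveys, no new data, visits or participants are needed. The linear model is standard in SPSS, the planned software.

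### The Mann-Whitney U test is assigned to median differences in self-efficacy and response-efficacy, but without an equal-shape assumption it tests whether scores tend to be higher in one arm

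*Combined protocol and SAP*

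**What the plan says.** Section 16, under Psychosocial Constructs Data Analysis, plans the comparison of two survey constructs in one sentence: "General linear models or Mann-Whitney U tests will be used to test mean or median differences for self-efficacy and response-efficacy". The arms compared are the pharmacist intervention and usual care. The two methods and the two targets are listed in the same order, so the natural reading is general linear model for means and Mann-Whitney U for medians.

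The arm sizes come from section 5: "90 participants will be enrolled in the study; 45 in the control group / 45 in the intervention group". Section 8 describes baseline and follow-up surveys.

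The documents do not give the response format, number of items or SD of these scores. They state no significance level for the comparison, no assumption that the two distributions share a shape, and no effect measure to accompany the rank test.

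**The concern.** The Mann-Whitney reference distribution is obtained by treating scores as exchangeable between arms, so its null is that the two distributions are identical. The test responds to departures of θ = P(CPVAC score > PCP score) + 0.5 P(tie) from 0.5. Equal medians do not imply θ = 0.5. They do so only under an added condition, such as equal shapes differing by a shift.

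On a score with few categories, answers can move up around the middle category while the median stays put. Followed as written, the plan would then support a claim of a difference in medians beside a table showing the same median in both arms. The reader would have no estimate of what the test had detected. At stake is what a significant result on these two constructs may be said to show.

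**Working it through.** The plan states no figure for this comparison, so there is none to reproduce. The only number from the documents is the sample size, 45 + 45 = 90. The 5-point score, the two-sided 5% level and every distribution below are assumptions.

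**1. One data set at the planned size**

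| Score | 1 | 2 | 3 | 4 | 5 | Total |
|---|---|---|---|---|---|---|
| PCP | 5 | 7 | 9 | 20 | 4 | 45 |
| CPVAC | 1 | 2 | 6 | 18 | 18 | 45 |

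*Medians (23rd ordered value).* Cumulative counts are 5, 12, 21, 41, 45 for PCP and 1, 3, 9, 27, 45 for CPVAC. The 23rd value is 4 in both arms.

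*Pairwise comparisons, 45 × 45 = 2,025.*
- CPVAC higher: 5×44 + 7×42 + 9×36 + 20×18 = 220 + 294 + 324 + 360 = 1,198.
- Tied: 5×1 + 7×2 + 9×6 + 20×18 + 4×18 = 5 + 14 + 54 + 360 + 72 = 505.
- PCP higher: 2,025 − 1,198 − 505 = 322.

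*Test.* U = 322 + 505/2 = 574.5, against an expected 2,025/2 = 1,012.5 under the null. With combined category totals 6, 9, 15, 38, 22, the tie term Σ(t³ − t) is 69,750. The variance is (2,025/12) × [91 − 69,750/(90×89)] = 13,887, so the SD is 117.8. Then z = (574.5 − 1,012.5)/117.8 = −3.72, and two-sided p = 0.0002 (no continuity correction).

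*What was detected.* θ = (1,198 + 505/2)/2,025 = 0.716. The means are 146/45 = 3.24 and 185/45 = 4.11, a difference of 0.87. The difference in medians is 0.

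**2. How often this could happen**

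Simulated rejection rates, 45 per arm, 10,000 replicates per case, equal population medians in every case:

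| Assumed distributions | θ | Rejects | Rejects with equal sample medians |
|---|---|---|---|
| Identical, 5-point | 0.50 | 5.2% | 4.1% |
| 5/15/25/40/15% vs 3/7/20/40/30%, medians 4 | 0.61 | 49% | 29% |
| 10/15/20/45/10% vs 2/5/13/40/40%, medians 4 | 0.71 | 96% | 65% |
| Symmetric 5-point, same centre, different spread | 0.50 | 6% | 1% |
| Continuous, exponential vs normal | not computed | 16% | not computed |

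With 36 per arm (an assumed 20% loss) the rejection rates are 4.6%, 40%, 91%, 7% and 14%.

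The test holds its level when the arms are identical and is barely disturbed by a symmetric difference in spread. It rejects often when scores are higher in one arm, even if the medians agree. The range depends entirely on the assumed distributions.

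**The case against.** The strongest reply is that the high rejection rates are power. Take a milder assumed pair, 3/10/25/42/20% against 2/6/17/45/30%, both with median 4. Mann-Whitney rejects in about 30% of trials. A reader might infer a false-positive rate six times the nominal 5%, or put the result down to unequal spread. Neither inference holds. The means are 3.66 and 3.95 and the SDs 1.00 and 0.94. The second arm is higher at every cut-point, with cumulative odds ratios of 1.52, 1.72, 1.84 and 1.71. A Welch comparison of means rejects about as often (28%). There is a real upward shift, which a coarse median hides and the test is right to detect. Nothing in the documents supports a claim that the planned test is invalid as a test of no effect at all.

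It can also be said that pairing means and medians in this way is common shorthand for a parametric or a rank-based comparison, that the plan does not fix how results will be worded, and that multi-item composite scores with similar shapes would make the mislabelling matter little. All of that is fair, and it limits the importance of the point.

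It does not remove it. The stated target for the rank test is a median difference, no equal-shape assumption is given, and the data set above shows a significant result with no median difference. Nor do the documents show that the linear model must be the sole main analysis; that would be a preference.

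**Conclusion.** The point stands as a mismatch between the stated hypothesis and the test. A significant Mann-Whitney result would support the statement that scores tend to be higher in one arm, but not by itself that the medians differ.

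The existence of the problem is shown by the worked data set, given a 5-point score. Its likely frequency cannot be determined, because the documents give neither the score format nor the expected distributions.

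The importance is minor. The comparison concerns two psychosocial constructs in a pilot of 90. The primary outcome, vaccine completion, is compared by a two-proportion Z test and is not affected.

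**What to change.** Remove the statement that Mann-Whitney tests medians, and tie each method to its own estimate. For example:

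*Self-efficacy and response-efficacy will be compared between the randomised arms. Where a general linear model is used, the difference in mean score will be reported with a 95% CI. Where the Mann-Whitney U test is used, it will be interpreted as testing whether scores tend to be higher in one arm, and P(CPVAC > PCP) + 0.5 P(tie) will be reported with a 95% CI.*

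This keeps both of the sponsor's methods. The cost is a short change of wording and no new data. The point estimate is U (counted for CPVAC) divided by the product of the arm sizes; in the example, (2,025 − 574.5)/2,025 = 0.716. The interval needs a little extra analysis. The downside is that the probability measure is less familiar to readers than a mean or median and needs a line of explanation.
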